⁷ Bloemen, M.C.T., et al., Prevention and curative management of hypertrophic scar formation. *Burns*, 2009. 35(4): p. 463-475.

Protocol version: 5

Template updated 5 Jul 2021

Methods and Measures

Design

This study is a randomized, controlled, within-subject trial examining the effectiveness of KeraStat Gel, as compared to the institutional SOC, Mepilex Ag, in improving wound cosmesis. Once the Investigator has determined the subject is a candidate for inclusion in the study, the subject will be approached about enrolling in this study. A total of 30 burn subjects presenting to the Burn Centers will be enrolled.

Upon presenting to the hospital, potential study subjects will be assessed for inclusion and approached for consent, as appropriate. Once the subject and/or legal guardian has consented to participate in the study, baseline assessments can be completed. We anticipate that the majority of subjects presenting with burns that qualify for inclusion in the study will have at least one night stay in the hospital; however, this is not criteria for inclusion. KeraStat Gel and Mepilex Ag will each be randomized to application on one of two identified burn sites on the subject, Burn A or Burn B. All subjects will have one burned area dressed with KeraStat Gel and a second area dressed with Mepilex Ag per SOC. The Investigator or study staff will initially apply the dressings per a computer-generated randomization scheme. The burn dressed with KeraStat Gel will have a secondary dressing of petrolatum gauze and telfa. For subjects who have more than two burns, all additional burns will be treated according to the physician's discretion. Subjects will be provided with enough KeraStat Gel and KeraStat Gel-related dressing supplies upon hospital discharge to accommodate prescribed dressing changes until their next visit. The Investigator will instruct subjects on dressing changes as required by institutional SOC guidelines and instructions for use of KeraStat Gel prior to discharge. The need to maintain treatment consistency will be stressed; Burn A and Burn B should always receive their designated dressing.

For the first 4 weeks, subjects will have weekly visits with site staff. On days 7 and 21, this visit will be remote. On days 14, and 28, this visit will be an office visit.

[figure not shown]

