During remote visits, adverse event recording will be recorded by the site. If the subject has agreed to the use of the Engage application on their phone, the subject will also complete a pain assessment for each burned area (Burn A and Burn B). For the Engage application, the subject number will be obtained for registration and completion of the e-diary. The subject will set up a personal identification number (PIN) and provide responses to security questions that will be used if they forget their PIN. The e-diaries will be completed via a web application on the mobile phone that is hosted in a database. As a Software-as-a-Service (SaaS) provider of clinical trial software and services, Clinical Ink acts as an agent on behalf of customers to collect Clinical Study Data. With respect to all Clinical Study Data, the collecting and processing of data are governed by the contractual relationship with each customer consistent with the notice provisions specified by the customer in their relationship with the individuals participating in the clinical study.

If the subject agrees to and is able, the subject will capture photographs of the wounds and upload to the MyChart application. Briefly, the subject will obtain the photograph and navigate to the MyChart application utilizing the web-browser on their phone. The subject should then navigate to the “Messaging” center and click “Ask a Question”. From here, the subject selects “New Medical Question.” The subject should choose their study physician and mark a “Visit Follow-Up Question”. They then can attach an image and click send.

During office visits on days 14 and 28, adverse event recording, incidence of infection, assessment of reepithelialization, photography, and a pain assessment will be completed for each burned area (Burn A and Burn B). A \$45 gas card (one per visit) and KeraStat Gel-related dressing supplies will be given to the subject during these visits, as well.

Partial thickness burns that do not require excision and grafting are expected to be fully closed within 21 days. Thus, after assessment at discharge, subjects will be followed bi-weekly until 4 weeks post-burn to ensure appropriate healing. Then, subjects will be seen at 3 months (± 7 days), 6 months (± 7 days), and 1 year (± 14 days) post-enrollment for site photographs and in order to assess the development of scarring using the Patient and Observer Scar Assessment Scale (POSAS), and TEWL measurements.

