Below is a schematic overview of the study.

Optional at-home questionnaire and photographs at virtual visits on weeks 1 and 3

Wound assessments, questionnaires, photographs, TEWL assessment at 3 months, 6 months, 1 year

Setting

This study will be conducted in the Wake Forest (WF) Burn Center and in the University Medical Center New Orleans (UMC). Subjects may continue treatment as inpatients or as outpatients.

Subjects Selection Criteria

- **Inclusion Criteria**

- Males and females, age 6 years and older
- Written informed consent and assent, if applicable (including parent if subject is a minor)
- Presenting with at least two comparable, discrete, and separate partial thickness thermal burns, as determined by the Investigator, measuring 50-1,000 cm² each
- Study wounds identified are partial thickness depth
- KeraStat Gel and Mepilex Ag can be applied to the randomized study burn wounds as definitive care treatment within 72 hours from time of injury
- Overall total body surface area (TBSA) burned < 20%

- **Exclusion Criteria**

- Pregnant or nursing
- Prisoner
- Presence of inhalation injury, as determined by the Investigator
- Injury requiring formal intravenous fluid resuscitation
- Concomitant non-thermal traumatic injuries
- Chronic medical conditions including, but not limited to, documented > renal impairment (Cr > 2.5 mg/dL), hepatic impairment (Total bilirubin > 2.5 mg/dL), thromboembolic disorders, active infection in study wound areas, uncontrolled diabetes (HbA1C > 7%), HIV infection, history of melanoma or systemic malignancy within the last 10 years
- Receiving corticosteroids, immunosuppressive agents, radiation or chemotherapy, topical growth factors, or any other medication the Investigator feels will affect wound healing
- Not expected to live at least 13 months post-burn
- Previously treated with a skin graft at either of the treatment sites

- Chemical or electrical burn
- Proposed study wounds are full thickness
- Any condition the Investigator determines will compromise subject safety or prevent the subject from completing the study

- **Sample Size**
The study size is 30 subjects, two wounds per subject, 30 wounds per treatment cohort resulting in 60 total wounds.

Because this trial is designed to examine long-term outcomes, no interim analyses or stopping rules are planned.

Interventions and Interactions

Intervention: KeraStat Gel

Agent description

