Ingredients: Water (Aqua), Oxidized Keratin, Carbopol, Phenoxyethanol, Ethylhexylglycerin, and Sodium Hydroxide. KeraStat Gel is for topical use only and should not be swallowed. Subjects should avoid contact with eyes. If swallowed, seek medical attention. If symptoms worsen or persist, consult a physician.

Agent Safety Data

KeraStat Gel has been subjected to a full suite of ISO 10993 safety testing (Table 1).

Table 1. Summary of Completed ISO 10993 Testing

Test ^{a,b}	Method	Test System	Route	Testing Outcome
Cytotoxicity	ISO 10993-5	Mouse fibroblast CCL-1 (L929)	In vitro	Non-cytotoxic
Sensitization	ISO 10993-10	Guinea Pig	Topical In vivo	Non-sensitizing
Irritation	ISO 10993-10	Rabbit (NZ White)	Intracutaneous In vivo	Mild-Moderate Irritant
Acute Systemic Toxicity (3 day)	ISO 10993-11	Mouse (Swiss Albino)	Intraperitoneal In vivo	Non-toxic
Subacute Systemic Toxicity (28 day)	ISO 10993-11	Rat (Albino)	Subcutaneous In vivo	Non-toxic

Pyrogenicity	ISO 10993-11	Rabbit (NZ White)	Intravenous In vivo	Non-pyrogenic
--------------	--------------	----------------------	-------------------------------	---------------

Performance testing, including *in vivo* testing of its application to burn wounds, supports the safety and reliable quality of this device. Two clinical studies have also supported product safety. This product is approved by the U.S. Food and Drug Administration (FDA) (K162759).

Agent Administration

In this clinical trial, subjects will apply KeraStat Gel as directed by the physician per institutional SOC guidelines. We anticipate that the medical care team or subject will clean and dress the wound every 1 to 3 days. KeraStat Gel should be changed at least every 3 days but can be changed as often as the Investigator feels is necessary. The wound should first be cleansed and debrided according to the institutional SOC guidelines. Following cleansing, KeraStat Gel should be applied uniformly, providing a coating across the entire surface of the burn and past the edge of the burn. On average, one tube of KeraStat Gel will cover 0.5% TBSA. At the time of dressing changes, KeraStat Gel should be removed with soap and water and gauze wiping (as necessary), reapplied, and covered with a secondary dressing of petrolatum gauze. Treatment will continue until full reepithelialization (100%) is achieved.

Interactions

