Dressings will be changed per institutional SOC guidelines but at a minimum of every 3 days. Subjects will return to the clinic on days 14 ± 3 and 28 ± 3 post-enrollment for the first 4 weeks and at months 3 (± 7 days), 6 (± 7 days), and 12 (± 14 days) post-enrollment. Subjects will also participate in a remote visit on days 7 ± 3 and 21 ± 3 post-enrollment. Dressing changes will be continued until reepithelialization is achieved. During each visit, study staff will document the number of dressing changes that occurred outside of clinic visits as well as any pertinent information related to the dressing changes. During visits when dressing changes are still necessary, subjects will complete the VAS pain score before and after dressing changes to each burn, and any unanticipated adverse events related to the device will be logged. Subjects who are able and willing will download an application on their smartphone that will prompt them to record the VAS pain score before and after dressing changes will complete this during remote visits on days 7 and 14. Subjects will also be asked to upload photos of the burns at days 7 and 21 utilizing the medical center's MyChart application. Appearance of the sites will be assessed at months 3, 6, and 12 using the POSAS. During the visits at 3, 6, and 12 months, sites will be subjected to 3 measurements of TEWL. Photographs will be obtained at all in-person visits and may be subjected to wound closure and percent epithelialization measurements via ImageJ. Recording of adverse events (AE), measurement of vital signs, examination of the wound/site of wound, and notation of concomitant medication and procedures will also take place during each visit. All measures will be completed if an individual agrees to a final visit after withdrawal from the study.

Masking

This study will be an open-label study.

Schedule of Events

Baseline Testing (All subjects)

- Photographs (prior to start of treatment)
- Vital signs (e.g., blood pressure, heart rate, temperature, height, weight)
- Examination of wound, including wound measurement
- Concomitant medications
- VAS pain score before and after dressing application

Discharge

- Adverse events

- Vital signs
- Examination of wound, including wound measurement and percent reepithelialization
- Photography of treatment site
- Concomitant medications and procedures
- Dressing change
- VAS pain score before and after dressing change

Day 7, 21 (± 3 , Remote visit)

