- Photography of treatment site on days 7 and 21 (optional)
- VAS pain score before and after dressing changes (optional)
- Adverse events

Day 14, 28 (± 3) Evaluation

- Adverse events
- Vital signs
- Examination of wound, including wound measurement and percent reepithelialization
- Photography of treatment site
- Concomitant medications and procedures
- Documentation of number and description of dressing changes since last visit (for subjects who do not participate in the optional tracking)
- Dressing change
- VAS pain score before and after dressing change

3 Month (± 7 days), 6 Month (± 7 days), 1 Year (± 14 days) Evaluation

- Adverse events
- Vital signs
- Examination of wound/site of wound, including wound measurement
- Photography of treatment site
- Concomitant medications and procedures
- POSAS
- TEWL

Early Termination Visit/Withdrawal from Study

- Adverse events
- Vital signs
- Examination of wound, including wound measurement
- Photography of treatment site
- Concomitant medications and procedures

- Dressing change (Month 1)
- VAS pain score before and after dressing change (Month 1)
- POSAS (Months 3-12)
- TEWL (Months 3-12)

Outcome Measure(s)

Assessments	Screening/Day 0	Discharge	Remote Follow-Up (Days 7 ±3 and 21 ±3)	First Month Follow-Up (Days 14 ±3, 28 ±3)	3 Month (±7 day), 6 Month (±7 day), 1 Year (±14 day) Follow-ups	Early Termination Visit
Written Informed Consent	X					
Demographic and Medical History	X					
Inclusion/Exclusion Criteria	X					
Randomization*	X					
Unanticipated Adverse Device Events		X	X	X		X
Adverse Events		X	X	X	X	X
Vital Signs	X	X		X	X	X
Examine Wound/ Site of Wound, including wound measurement	X	X		X	X	X
Photography of Treatment Sites	X	X	X**	X	X	X
Concomitant Medications	X	X		X	X	X
Concomitant Procedures		X		X	X	X
Dressing Changes	As needed	As needed	As needed	As needed		
VAS Pain Score	X	X	X**	X		X
Wound Closure (Investigator assessment)				X		X
Percent epithelialization				X		X

Assessments	Screening/Day 0	Discharge	Remote Follow-Up (Days 7 ±3 and 21 ±3)	First Month Follow-Up (Days 14 ±3, 28 ±3)	3 Month (±7 day), 6 Month (±7 day), 1 Year (±14 day) Follow-ups	Early Termination Visit
(Investigator assessment)						
Cosmesis of Treatment Sites (POSAS)					X	X
TEWL					X	

*Randomization will occur after confirmation of inclusion and exclusion criteria.

**These activities will be optional and dependent on whether subject has resources for use of an at-home application.

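### Dressing-change pain at days 14 to 28 may be scored only while burns are unhealed, and at days 7 and 21 only by app users: the late comparison can be biased either way and the day 7 one is imprecise

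*Combined protocol and SAP*

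**What the plan says.** Pain at dressing changes and speed of reepithelialization are both secondary objectives (Objectives). The comparison is within subject: "All subjects will have one burned area dressed with KeraStat Gel and a second area dressed with Mepilex Ag per SOC". The Sample Size entry reads "The study size is 30 subjects, two wounds per subject, 30 wounds per treatment cohort resulting in 60 total wounds".

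**When pain is scored in clinic.** Interactions: "During visits when dressing changes are still necessary, subjects will complete the VAS pain score before and after dressing changes to each burn". Agent Administration: "Treatment will continue until full reepithelialization (100%) is achieved". Design: "Partial thickness burns that do not require excision and grafting are expected to be fully closed within 21 days". However, Design also lists a pain assessment of Burn A and Burn B among the day 14 and 28 procedures without any condition. In the schedule table, dressing changes are marked as needed while the VAS at days 14 and 28 has a plain X.

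**When pain is scored remotely.** Design: "If the subject has agreed to the use of the Engage application on their phone, the subject will also complete a pain assessment". The footnote to the schedule table says of the remote VAS and photographs: "These activities will be optional and dependent on whether subject has resources for use of an at-home application". Adverse events are recorded by the site at the same remote visits for everyone. Interactions says app users "will complete this during remote visits on days 7 and 14", whereas Design, Schedule of Events and Outcome Measure(s) give days 7 and 21, and day 14 is an office visit.

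**What is analysed.** The Analytical Plan uses the VAS at Screening and days 7, 14, 21 and 28, with box plots and a Kruskal-Wallis test. Discharge VAS is scheduled for both burns but is not among these time points. There is no rule for a burn that has healed, for a subject with one burn still dressed, or for a subject without the app. The extent of missing data is to be described and interpreted.

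**The concern.** Two separate mechanisms thin out the pain data, and they do different harm.

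**Healing acts on the burn.** If the VAS is taken only while dressing is still needed, whether a score exists depends on a post-randomization outcome. If one dressing heals faster, the burns left under it at day 14 are a more severe selection than those left under the other, and randomization no longer protects the comparison. Keeping only subjects with both burns still dressed does not cure this, because it also selects on healing. By the protocol's own 21-day expectation, few scores at days 21 and 28 would be dressing-change scores at all.

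**App use acts on the subject.** Each app user supplies both burns, so the arms stay balanced. The cost is fewer pairs and a less representative group, and it falls on day 7, the fixed post-baseline time at which healing has removed the fewest burns.

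The secondary pain question therefore rests on late scores that may be selected and on a day 7 sample of unknown size. The primary POSAS analysis is not affected.

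**Working it through.** **Plan's own figure.** 30 subjects × 2 wounds = 60 wounds, which agrees with the text. The documents give no alpha, power, effect size or SD for pain, so 30 cannot be reproduced from a formula. Everything below except the 30 pairs is an assumption.

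**Step 1: how the set shrinks.** A simulation of 200,000 subjects assumed median healing of 16 days on both dressings, or 16 days on SOC and 13 on KeraStat. The expected number of the 30 subjects with both burns still dressed is:

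| Day | 16 v 16 days | 16 v 13 days |
|---|---|---|
| 7 | 29.5 | 28.6 |
| 14 | 14 | 9.5 |
| 21 | 2.4 | 1.1 |
| 28 | 0.3 | 0.1 |

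**Step 2: size of the selection effect when KeraStat heals faster.** Let severity S be normal with SD 1, mean 0 for SOC and mean −0.30 for KeraStat, and let a burn stay dressed while S > c. The mean severity of a dressed burn is μ + φ(c − μ)/[1 − Φ(c − μ)]. At c = 0 this is 0.798 for SOC and 0.698 for KeraStat, a difference d = 0.100. Let pain correlate r with severity and fix the total true benefit at 0.30 SD, with the part not explained by severity acting directly. The observed benefit is then 0.30 − r(0.30 − d).

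| c | SOC burns unhealed | d | r = 0.3 | r = 0.5 | r = 1 |
|---|---|---|---|---|---|
| −0.5 | 69% | 0.134 | 0.25 | 0.22 | 0.13 |
| 0 | 50% | 0.100 | 0.24 | 0.20 | 0.10 |
| 0.5 | 31% | 0.074 | 0.23 | 0.19 | 0.07 |

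The range 0.07 to 0.13 SD thus needs r = 1. Restricting to pairs with both burns unhealed (c = 0, r = 1) gives about 0.14 SD for a within-subject correlation of 0.3 and 0.18 SD for 0.6, which is still below 0.30.

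**Step 3: direction.** The simulation of Step 1, with a true benefit of 1.0 cm or none and two assumed non-zero strengths of the severity-pain link, gives these unpaired day 14 differences among dressed burns (SOC minus KeraStat):

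| Healing | True 1.0 cm | True 0 |
|---|---|---|
| KeraStat faster (13 v 16 days) | 0.77 to 0.56 | −0.22 to −0.45 |
| Equal | 1.0 | 0 |
| KeraStat slower (16 v 13 days) | 1.22 to 1.42 | +0.22 to +0.43 |

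With no severity-pain link the bias is zero in every row. At day 7 the true 1.0 cm appears as 0.93 to 0.97 if KeraStat heals faster and 1.03 to 1.08 if slower, so healing barely disturbs day 7.

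**Step 4: precision at day 7.** App uptake of 40% to 70% gives 0.4 × 30 = 12 to 0.7 × 30 = 21 pairs. For a paired t-test (noncentral t, two-sided 0.05, 80% power), the detectable difference in SDs of paired differences is 0.53 with 30 pairs, 0.64 with 21 and 0.89 with 12.

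**Step 5: what full capture would buy.** A benefit of 0.30 SD per burn, with within-subject correlation ρ, equals 0.30/√[2(1 − ρ)] SDs of the difference: 0.25 at ρ = 0.3 and 0.34 at ρ = 0.6. Power with all 30 pairs is 27% and 43%.

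**The case against.** The condition on dressing rests on one sentence in Interactions. Design and the schedule table can be read as requiring a score for each burn at days 14 and 28 regardless, and the sentence itself may apply to the visit and not to the burn. This stands: the documents show an inconsistency, not a settled rule. The unconditional reading does not remove the problem, though. Scores from healed burns with no dressing change would then mix with dressing-change scores, and no rule says how to treat them.

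A reader might infer that the design hides a true KeraStat benefit. The documents do not support that. Attenuation needs KeraStat to heal faster, which is the trial's hypothesis and not a known fact, and slower-healing burns to hurt more. With slower KeraStat healing the same mechanism flatters it. A large attenuation also needs pain to follow severity perfectly, whereas the Background suggests a direct route to pain through dressings that adhere to the wound.

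Nor is pain recorded only for dressed burns and app users: baseline and discharge scores are scheduled on both burns. And app use should not be read as biasing the treatment contrast, because it selects subjects and not burns.

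Finally, pain at a dressing change has no meaning once dressing has stopped, and a separate SAP is still to be finalised before database lock. It can supply the missing rule, but it cannot recover day 7 scores that were never requested.

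**Conclusion.** The point holds in a limited form. Under the Interactions wording, the pain comparison at days 14 to 28 is conditional on non-healing; at days 7 and 21 it is conditional on app use under every wording. The sign of the late bias is unknown: attenuation if KeraStat heals faster and worse burns hurt more, an exaggerated or spurious benefit if it heals slower, none if healing is equal or pain is unrelated to severity. In the faster-healing case, moderate correlations take away roughly 0.05 to 0.11 of a 0.30 SD benefit (0.30 − 0.25 and 0.30 − 0.19). The app restriction is a loss of precision and generalizability.

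Healing times, severity model, correlations and app uptake are all assumptions; only the 30 pairs come from the documents. This is a secondary endpoint, and the change is worth making because it is cheap, not because the trial's main conclusion is at risk.

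**What to change.** 1. At the existing day 7 and 21 remote contacts, have site staff ask every subject for the 0-10 scores before and after the latest dressing change, for each burn. Keep the app as an option and record the mode of collection.
2. Add the discharge VAS, already collected, to the pain time points in the Analytical Plan. Its day varies by subject but is the same for both burns.
3. Make day 7, with discharge, the main pain comparison, analysed as the within-subject paired difference. The Kruskal-Wallis test treats scores as independent and does not use the pairing.
4. Show days 14 to 28 as supportive, with the number of burns no longer dressed in each arm at each visit.
5. Reconcile the Interactions sentence with Design and the schedule table on when day 14 and 28 pain is scored, and state how a healed burn is handled. Reconcile the app days in Interactions with those given elsewhere.

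**Cost.** A few minutes per existing contact, plus protocol and SAP wording; no added visit and no change to treatment. A recalled spoken score is not the same as a marked line with facial anchors, which matters in subjects from age 6. The study is open-label, so recall error may not be equal for the two burns. Full capture improves precision but, as Step 5 shows, does not make the trial well powered for small pain differences.

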Photographs will be obtained during each subject contact. Photos will be obtained from a distance of approximately 18 inches (if possible) so as to encompass each burn in its entirety. A ruler will lay flush with adjacent uninjured skin and will be included in each picture. Cameras and downloading capabilities should be tested prior to enrolling the first subject. Only jpeg images taken with a digital camera will be accepted. Photographs are a requirement of participation in this clinical trial. Optional photographs will be collected on days 7 and 21 by subjects who are able and willing to upload photos utilizing the institution's MyChart application.

Additional points:

Baseline photographs must be taken after informed consent but prior to randomization.

Images will be transferred from the site's camera to the patient portal. The file naming convention is Patient Acrostic_Burn ID_Visit Number.

At the visit where complete wound closure is documented, the photographs of the burns may be subjected to analysis using ImageJ to confirm wound closure.

Study Subject Withdrawal

Subjects may withdraw from study participation at any time. Decision to withdraw should be noted on the CRF including the date and reason. Study staff should ask subject if he/she will agree to a final visit, and this should be noted on the CRF as well.

Analytical Plan

Descriptive statistics for continuous variables and frequency counts and percentages for categorical demographics variables will be summarized by subject and by burn treatment group. Listings will be created for all data by Case Report Form. A Statistical Analysis Plan (SAP) that includes mock tables, listings and figures (TLFs) will be developed and finalized prior to the lock of the clinical database. The extent to which missing data occurs will be described with an interpretation of the extent on the impact of the analysis as well as generalizability of the data.

Statistical analyses will be conducted for two analysis populations.

- a. Intention to treat: All subjects randomized will be included in the analyses.
- b. Safety: All subjects that have received one or more treatment applications will be included in the safety analysis for all safety endpoints.

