For the primary objective of the study, improved cosmesis will be analyzed using data from the POSAS, as a total score, and separately for the observer score and then the subject score. Changes from baseline will be examined at 3 months, 6 months and again at 1 year post treatment. TEWL will be considered at 3 months, 6 months, and 1 year. This analysis may also consider the baseline status of the burn including depth, surface area, location of the burn injury and subject baseline characteristics (age, concomitant injury).

Protocol version: 5

Template updated 5 Jul 2021

Secondary objectives include determining whether KeraStat Gel wound dressing results in less painful dressing changes, faster reepithelialization, and reduction in need for excision and grafting. Improvement in pain will be assessed using the scoring from the VAS pain scale at Screening, Days 7, 14, 21 and 28. Box plots of the VAS pain scores will be presented displaying the medians and quartiles in each treatment group over time. A nonparametric test will be used to determine changes in the score across time (Kruskal-Wallis) as well. Reductions in excision and grafting will be analyzed by treatment groups using the same methods as the VAS pain score. Median time to 100% reepithelialization by study treatment group will be conducted, mean times (days) will be analyzed using a Wilcoxon test by treatment groups, as well as a time to event analysis for 90% or higher reepithelialization from baseline.

The incidence of adverse events will be reported and summarized by treatment group. Adverse events will be coded in MedDRA by system organ class and preferred terms (PT).

Human Subjects Protection

Subject Recruitment Methods

Subjects who present at the Burn Center at WF or UMC with qualifying burns as determined by the Investigator will be approached for inclusion in the study by study personnel.

Remuneration

Enrolled study subjects will be provided with one \$45 gas card per visit for office visits on days 14 and 28 and months 3, 6, and 12.

Informed Consent

All subjects must give their informed consent in accordance with the informed consent regulations in Title 21 CFR, Part 50. Each subject over 18 years and subjects under 18 and their legally authorized representative will execute written informed consent (and assent if applicable) before any study procedures are conducted. Study personnel will obtain written informed consent in the clinic.

Confidentiality and Privacy

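### The primary objective rests on three POSAS scores at three visits with no deciding comparison named, and its stated measure, change from baseline, cannot be formed for POSAS

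*Combined protocol and SAP*

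**What the plan says.** The Objectives section states the primary objective only as improved cosmesis of healed wounds. The Analytical Plan makes it operational as follows: "improved cosmesis will be analyzed using data from the POSAS, as a total score, and separately for the observer score and then the subject score". The next sentence gives the measure and the times: "Changes from baseline will be examined at 3 months, 6 months and again at 1 year post treatment". The same paragraph adds "TEWL will be considered at 3 months, 6 months, and 1 year", without saying whether TEWL is primary or supportive. Covariate adjustment is optional.

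On when POSAS is collected, the Interactions section says "Appearance of the sites will be assessed at months 3, 6, and 12 using the POSAS". The Outcome Measure(s) table marks POSAS at the 3-month, 6-month and 1-year visits and at early termination, not at Screening/Day 0. The early-termination list limits it to months 3 to 12.

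A separate SAP is promised, which "will be developed and finalized prior to the lock of the clinical database". It is not among the documents. On masking: "This study will be an open-label study".

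**The concern.** A primary objective needs one comparison, or an ordered set, whose result settles it. Here three scores at three visits stand side by side. Suppose the subject score favours KeraStat at month 12 and the observer score does not, or the total is significant at month 3 and not at month 12. Nothing in the protocol says which result decides. The choice would then have to be made later, in an open-label trial where month-3 and month-6 scores with known treatment can already exist before the SAP has to be final.

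The change-from-baseline measure is a distinct fault in the same paragraph. It does not create the multiplicity, but that sentence must be rewritten anyway, because the quantity it names does not exist for POSAS as scheduled.

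**Working it through.** **Plan's own figures.** Sample Size gives 30 subjects with two wounds each: 30 × 2 = 60 wounds, which checks. No alpha, sidedness, power, effect size, SD, correlation or dropout is stated, so 30 cannot be re-derived.

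**Count.** 3 scores × 3 visits = 9 POSAS comparisons; with TEWL at three visits, 12.

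**What the protocol fixes.** The Analytical Plan names Kruskal-Wallis for pain and Wilcoxon for healing time, both secondary. For POSAS it names no test.

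**Baseline.** Change from baseline needs a day-0 POSAS value. The first scheduled value is at month 3, so it cannot be computed.

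**Illustration of size.** All of the following are assumptions: 30 complete pairs, paired t-tests at two-sided 0.05, total = observer + subject, and (between-visit, observer–subject) correlations of the paired differences of (0.3, 0.3), (0.5, 0.5), (0.8, 0.7) and (0.9, 0.9).

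Reference if tests were independent: 1 − 0.95^9 = 0.370 for nine and 1 − 0.95^3 = 0.143 for three. The scores are correlated and the total contains the other two, so these are upper references.

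*No true effect, at least one significant result (200,000 simulated trials per setting):*

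| Setting | Any of nine, two-sided | Any of nine, favouring KeraStat | Total over 3 visits, two-sided | Total over 3 visits, favouring KeraStat |
|---|---|---|---|---|
| 0.3, 0.3 | 0.276 | 0.141 | 0.137 | 0.069 |
| 0.5, 0.5 | 0.235 | 0.118 | 0.126 | 0.063 |
| 0.8, 0.7 | 0.166 | 0.084 | 0.098 | 0.050 |
| 0.9, 0.9 | 0.119 | 0.060 | 0.085 | 0.042 |

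Against 0.05, nine comparisons give 0.119/0.05 = 2.4 to 0.276/0.05 = 5.5 times the nominal risk. The total alone gives 0.085/0.05 = 1.7 to 0.137/0.05 = 2.7 times. Dropping the total-as-sum assumption and using only the six observer and subject comparisons gives 0.117 to 0.251 two-sided.

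*Uniform true effect (40,000 trials per setting).* A paired t-test with n = 30 at two-sided 0.05 has 80% power at 0.529 SD of the paired difference. That effect is put on the total at every visit and shared equally by observer and subject scores. With observer–subject correlation r, each component effect is 0.53 × √(2 + 2r) / 2, which is 0.43 SD at r = 0.3 and 0.52 SD at r = 0.9. Proportion of trials in which some but not all results significantly favour KeraStat:

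| Setting | Nine results | Total over visits | Three month-12 scores |
|---|---|---|---|
| 0.3, 0.3 | 0.856 | 0.404 | 0.425 |
| 0.5, 0.5 | 0.708 | 0.345 | 0.320 |
| 0.8, 0.7 | 0.458 | 0.217 | 0.216 |
| 0.9, 0.9 | 0.273 | 0.154 | 0.111 |

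*What kind of disagreement.* Under the same assumptions, a significant result favouring KeraStat together with any of the nine estimates pointing the other way occurs in 0.01% to 4.8% of trials. The total being significant at month 3 and not at month 12 occurs in about 5% to 14%. Month-12 observer and subject scores differ in significance in 11% to 38%.

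**The case against.** **The total is listed first, so it leads.** List order is not a stated hierarchy. Even if it were, the visit remains open and the 8% to 14% figure applies.

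**Month 12 is implied.** Sample Size says "Because this trial is designed to examine long-term outcomes, no interim analyses or stopping rules are planned", and Data and Safety Monitoring asks that the 12-month forms be completed at termination. Both lean towards month 12. But the first explains the absence of interim analyses, the second is about data collection, and neither designates a deciding visit.

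**The SAP will settle it.** It may, and this limits what can be said about the eventual analysis. The protocol does not list a primary comparison or multiplicity rule among the SAP's contents, and finality is required only before lock. No document says that anyone reviews scores by treatment before then, so the exposure is an opportunity, not a finding.

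**Stronger readings a reader might infer.** One is that disagreement is likely. The narrower comparisons give 11% to 43%, and the nine-way figure exceeds one half only at the two lower correlation settings. Some of the discordance is built in, because each component has less power than the total. Another is that the trial's false-positive risk is 2 to 6 times nominal. That needs an any-one-wins rule at 0.05 per test, and the documents state neither. These objections stand against the size, not against the omission.

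**Conclusion.** The point holds, and should be fixed. Two parts rest on the text alone: the plan names no comparison that decides the primary objective, and its stated measure is not computable for POSAS as scheduled. So mixed significance would leave the primary objective undecided. Such a result is possible, not shown to be likely: about 11% to 86% under a uniform 0.53 SD effect. It would mostly be threshold discordance, not evidence of opposite effects.

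The false-positive figures (12% to 28% over nine comparisons, 8% to 14% for the total over visits, both two-sided) are conditional on counting any one favourable result at an assumed 0.05. They rest on assumed correlations, complete pairs and, where the total is used, a total that is the sum of the two scores. They illustrate what an unspecified rule could cost and do not describe a rule the sponsor has adopted.

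**What to change.** Before outcome data by treatment are reviewed, amend the Analytical Plan:

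1. For POSAS, replace change from baseline with the within-subject KeraStat minus Mepilex Ag difference.
2. Name one primary comparison. Example: total POSAS at month 12, with the total defined, by a named paired test at two-sided 0.05. One pre-specified repeated-measures estimate over the three visits would also serve.
3. Test the observer and subject scores next in fixed sequence, each only if the preceding test is significant.
4. Report the other visits and TEWL as supportive, with 95% confidence intervals.
5. State how missing pairs are handled.

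Checked by simulation with no true effect (100,000 trials), the fixed sequence starting from the month-12 total gives a two-sided error of 0.049 to 0.051. A test of the mean total over three visits gives 0.050 to 0.051. Bonferroni over nine is the costly route: 0.05/9 = 0.0056 per test raises the effect detectable with 80% power from 0.53 to 0.71 SD, and power at 0.53 SD falls from 80% to about 48%.

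Cost: no added visits or subjects, but the protocol change must be reported to the IRB. With month 12 as primary, a benefit seen only at month 3 or 6 becomes supportive. A month-12 comparison is also the most exposed to missing pairs; the repeated-measures option uses all visits.
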